**Table TTT. Systolic Blood Pressure over Time** 

mmHg	Placebo	4P004	4P004	4P004	4P004	4P004
	(pooled)					(pooled)
	(N=XX)	(N=XX)	(N=XX)	(N=XX)	(N=XX)	(N=XX)
Baseline						
Value						
n	XX	XX	XX	XX	XX	XX
mean (SD)	XX (XX)					
()						
1h Post-Dose						
Value						
n	XX	XX	XX	XX	XX	XX
mean (SD)	XX (XX)					
()						
Change from BL						
n	XX	XX	XX	XX	XX	XX
mean (SD)	XX (XX)					
()						
PCSA						
≤ 95 + decrease from baseline ≥ 20	XX (XX.X%)					
≥ 160 + increase from baseline ≥ 20	XX (XX.X%)					
No PCSA	XX (XX.X%)					
()						

#### **Table TTT. Heart Rate Pressure over Time**

### 12.6 Electrocardiograms (ECG)

The 12-lead ECG parameters are Heart Rate, PR, QRS and QT. They are measured at the following times: Screening (D-7), D1 (T0-15min and T0+12h).

They will be presented with the same layout as Vital Signs, at Baseline and 12 hours post-baseline. The relative change from baseline will be added.

Table TTT. ECG: Hear Rate over Time

Table TTT. ECG: PR over Time

Table TTT. ECG: QRS over Time

Table TTT. ECG: QT over Time

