## 3.2 Endpoints

#### 3.2.1 Primary endpoints

- Number of Adverse events (AEs), serious AEs (SAEs) (Common Terminology Criteria Adverse Events [CTC-AE]) from ICF signature to D29, including target knee pain and tenderness, erythema, swelling, local pain at injection site.
- Vital signs from D-7 to D8, ECG from D-7 to D1: Mean change, number of Potentially Clinically Significant Abnormality (PCSA), Percentage of participants with PCSA
- Laboratory changes (Red Blood Cells (RBC), White Blood Cells (WBC), Hemoglobin (Hb), platelets, alanine transaminase (ALT), aspartate transaminase (AST), glycemia, amylasemia, creatinin clearance) from D-7 to D8: Mean changes number of PCSA, Percentage of participants with PCSA.

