## Stopping rules

The study will be immediately suspended, and no additional IMP administered pending review and discussion of all appropriate study data by the DSMB if 1 or more participants develop any of the following adverse events deemed to be possibly, probably, or definitely related to the IMP by the Investigator and/or Medical Monitor, based upon close temporal relationship or other factors:

- Severe local reaction within 7 days after injection
- Clinical manifestations of hypoglycemia
- Severe gastro-intestinal adverse event
- Potentially clinically significant ECG abnormalities.
- Any serious adverse event considered reasonably related to the IMP (SAR) by the Principal Investigator.

The study will not be restarted until all parties have agreed to the course of action to be taken and the EC has been notified.

Dose limiting toxicity (DLT) describes side effects of a drug that are serious enough to prevent an increase in dose or level of that treatment.

When more than 1 DLT occurs in a dosing cohort, dose escalation must be stopped and this dose level will be identified as the non-tolerated dose.

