### 10.1.4 Safety analysis

The safety evaluation will be based upon the review of the individual values (clinically significant abnormalities), descriptive statistics (summary tables, figures) and, if needed, on statistical analysis (appropriate estimations, confidence intervals). No statistical significance tests will be performed on safety data.

Potentially clinically significant abnormality (PCSA) values are defined as abnormal values considered medically important by the Sponsor, according to predefined criteria/thresholds based on literature reviews and defined by the Sponsor for clinical laboratory tests, vital signs, and ECG parameters.

All safety data will be presented in listings and will be summarized by placebo, each 4P-004 dose level, 4P-004 overall, and overall total.

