### 9 General Principles for Statistical Analysis

Data will be summarized using classical descriptive statistics for the following groups:

- pooled placebo (i.e. participants receiving placebo in any cohort),
- each 4P004 dose level,
- unplanned doses if any (see below),
- 4P004 overall

A group "All" (Placebo + 4P004 overall) will be added if explicitly mentioned.

Categorical data will be presented using counts and percentages of subjects, while continuous variables will be presented using the mean, standard deviation, median, minimum, maximum, and number of observations with non-missing values. The coefficient of variation [%CV] will be provided for PK parameters.

The safety evaluation will be based upon the review of the individual values and descriptive statistics. No statistical significance tests will be performed on safety data.

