#### 16 References

ICH Guidance Topic E9 "Statistical Principles for Clinical Trials"

# 17 Tables, Figures & Listings in CSR Section 14

The following tables will be included in the report either in the text or in a dedicated chapter reporting all tables but not included in the text.

Туре	Number	Title	Population
Table	1.1	Participant disposition	All
Table	1.2	Deviations by Category	Safety
Listing	1.2.1	Major Deviations	Safety
Table	1.3	Demographics and Baseline Characteristics	Safety
Table	1.4	Other Baseline Characteristics	Safety
Table	1.5.1	Pain killers started and ended before treatment	Safety
Table	1.5.2	Other medications started and ended before treatment	Safety
Table	1.6	Medical History by SOC	Safety
Table	2.1	Pain killers started before treatment and continuing at IMP injection	Safety
Table	2.2	Pain killers started during treatment	Safety
Table	2.3	Other medications started before treatment and continuing at IMP injection	Safety
Table	2.4	Other medications during treatment	Safety
Table	3.1	Overview of TEAEs	Safety
Table	3.1.1	TEAEs by SOC and PT	Safety
Table	3.1.2	TEAEs by SOC, PT and Toxicity Grade	Safety
Table	3.1.3	TEAEs by SOC, PT and Relationship to Study Drug	Safety
Table	3.2	Treatment-Emergent AESIs by SOC and PT	Safety
Table	3.2.1	Treatment-Emergent AESIs by SOC, PT and Toxicity Grade	Safety
Listing	3.2.2	Treatment-Emergent AESIs	Safety
Table	3.3	Injection Site Reactions	Safety
Listing	3.4	Serious Adverse Events	Safety
Listing	3.5	Deaths	Safety
Table	4.1	Target Knee Pain from Pre-Dose to 24h Post-Dose	Safety
Table	4.2	Target Knee Pain from Visit 2 to End of Study	Safety
Table	4.3	Target Knee Pain from Visit 2 to Day 8	Safety
Table	5.0	Weight over Time	Safety
Table	5.1	Systolic Blood Pressure over Time	Safety
Table	5.2	Diastolic Blood Pressure over Time	Safety
Table	5.3	Heart Rate over Time	Safety
Table	6.1	ECG: Heart Rate over Time	Safety
Table	6.2	ECG: PR over Time	Safety
Table	6.3	ECG: QRS over Time	Safety
Table	6.4	ECG: QT over Time	Safety
Table	7.1	Hematology over Time	Safety
Table	7.1.1	Hematology PCSA over Time	Safety
Table	7.2	Chemistry over Time	Safety
Table	7.2.1	Chemistry PCSA over Time	Safety
Table	7.3	Glycemia over Time	Safety
Table	8.1	Plasma Concentrations over Time	PK
Figure	8.1.0.3	Plasma Concentrations over Time by Subject -	PK
Figure	8.1.1	Plasma Concentrations over Time by Subject -	PK
Figure	8.1.2	Plasma Concentrations over Time by Subject -	PK
Figure	8.1.3	Plasma Concentrations over Time by Subject -	PK

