# 19 Potentially Clinically Significant Abnormalities

Potentially clinically significant abnormality (PCSA) values are defined as abnormal values considered medically important by the Sponsor, according to predefined criteria/thresholds based on literature reviews and defined by the Sponsor for clinical laboratory tests, vital signs, and ECG parameters.

When possible, PCSA will be computed at baseline or before.

Parameter	PCSA	Comments
Chemistry		
AST or ALT	> 3 ULN	Guidance for Industry Drug-Induced Liver Injury FDA, 2009
Potassium	< 3 mmol/L or ≥ 5.5 mmol/L	
CLcr (mL/min) (Estimated creatinine clearance based on the Cokcroft Gault equation)	< 15 (end stage renal disease) ≥ 15 - < 30 (severe decrease in GFR) ≥ 30 - < 60 (moderate decrease in GFR)	FDA draft Guidance 2020 Pharmacokinetics in Patients with Impaired Renal Function Study Design, Data Analysis, and Impact on Dosing
Amylasemia	≥ 1.5 ULN	
Glycemia	< 70 mg/dL	DSMB
Hematology		
RBC	≥ 6 Tera/L	
Hb	≤ 115 g/L (Male); ≤ 95 g/L (Female) ≥ 185 g/L (Male); ≥ 165 g/L (Female) Decrease from Baseline ≥ 20 g/L	Criteria based upon decrease from baseline are more relevant than based on absolute value.
WBC	< 3.0 Giga/L (Non-Black) < 2.0 Giga/L (Black) ≥ 16.0 Giga/L	
Lymphocytes	> 4.0 Giga/L	
Neutrophils	< 1.5 Giga/L (Non-Black); < 1.0 Giga/L (Black)	International Consensus meeting on drug- induced blood cytopenias, 1991. FDA criteria.
Monocytes	> 0.7 Giga/L	
Basophils	> 0.1 Giga/L	
Eosinophils	> 0.5 Giga/L	Harrison- Principles of internal Medicine 17th Ed., 2008
Platelets	< 100 Giga/L ≥ 700 Giga/L	International Consensus meeting on drug- induced blood cytopenias, 1991.
Vital Signs		
HR (bpm)	≤ 50 + decrease from baseline ≥ 20 ≥ 120 + increase from baseline ≥ 20	
SBP (mmHg)	≤ 95 + decrease from baseline ≥ 20 ≥ 160 + increase from baseline ≥ 20	
DBP (mmHg)	≤ 45 + decrease from baseline ≥ 10 ≥ 110 + increase from baseline ≥ 10	
ECG		
HR (bpm)	< 50 < 50 + decrease from baseline ≥ 20 > 100 > 100 + increase from baseline ≥ 20	
PR (ms)	> 200 > 200 + increase from baseline ≥ 25%	
QRS (ms)	> 110 > 110 + increase from baseline ≥ 25%	
QT (ms)	> 500

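### The SAP summarises only uncorrected QT, with no pre-specified QTc, so a drug-related heart-rate change can hide or imitate a QT effect in a primary ECG endpoint

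*SAP*

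**What the plan says.** Protocol section 3.2.1 places ECG among the primary endpoints: "Vital signs from D-7 to D8, ECG from D-7 to D1: Mean change, number of Potentially Clinically Significant Abnormality (PCSA", together with the percentage of participants who have one. Protocol section 10.1.4 asks for descriptive changes from baseline and names no rate correction. Section 8.1.3 takes the values from the device's automatic reading, subject to investigator review, and is also silent on correction.

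SAP section 12.6 lists the variables: "The 12-lead ECG parameters are Heart Rate, PR, QRS and QT". On layout it says: "They will be presented with the same layout as Vital Signs, at Baseline and 12 hours post-baseline". It adds relative change to the absolute change. The table list in SAP section 17 follows the same four variables in Tables 6.1 to 6.4, and the last of them is "ECG: QT over Time". There is no QTc table, and QTc appears in neither abbreviation list.

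In SAP section 19 the only QT criterion visible is raw QT above 500 ms. ECG heart rate, PR and QRS each also have a criterion that uses change from baseline; for QRS it reads "> 110 + increase from baseline ≥ 25" percent. The text available to us ends at the QT row, so a further QT criterion may have been lost. The point does not depend on that row, because section 12.6 and the table list establish the gap on their own.

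**The concern.** QT depends on heart rate. If the drug changes heart rate, raw QT changes even when repolarisation does not. A rate increase shortens raw QT and can conceal a true prolongation. A rate decrease lengthens it and can look like one.

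The planned comparison does not remove this. The comparator column is "pooled placebo (i.e. participants receiving placebo in any cohort"), which cancels rate changes that both arms share (from time of day, hospital stay or the injection procedure) but leaves any change caused by the drug. The separate ECG heart-rate table shows the group-level shift, but no planned output combines QT with heart rate within a participant.

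The consequence is a QT summary, within a primary safety endpoint, that cannot be read without a further analysis the plan does not specify.

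**Working it through.** **Inputs.** The documents give the variables, the single post-dose summary time (12 h) and the comparator. They state no QT figure to reproduce and no heart-rate effect of the drug. Three assumptions are therefore needed: baseline heart rate (HR) 65 bpm, baseline corrected QT 410 ms, and a drug-related shift between -10 and +15 bpm.

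**Formula.** Fridericia: QTcF = QT / (60/HR)^(1/3), so raw QT = QTcF × (60/HR)^(1/3).

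**Baseline.** 410 × (60/65)^(1/3) = 399.2 ms.

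**Step 1: no true effect (QTcF stays at 410), only heart rate changes.**

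| HR change (bpm) | HR at 12 h | Raw QT change (ms) |
|---|---|---|
| -10 | 55 | +22.9 |
| -5 | 60 | +10.8 |
| +5 | 70 | -9.7 |
| +10 | 75 | -18.6 |
| +15 | 80 | -26.7 |

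This is roughly 2 ms of raw QT per bpm.

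**Step 2: true rise that raw QT hides completely.** Raw QT is unchanged when QTcF rises by 410 × [(HR at 12 h / 65)^(1/3) - 1].

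- +5 bpm: 10.3 ms
- +10 bpm: 20.0 ms (19.1 ms if baseline QTcF is 390, 21.0 ms if it is 430)
- +15 bpm: 29.4 ms

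**Step 3: does placebo remove it?** Let placebo go from 65 to 70 bpm and active from 65 to 80, with no true effect in either arm. The raw changes are -9.7 and -26.7 ms, so active minus placebo is -17.0 ms. If both arms rise equally, the difference is 0.

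**Step 4: does the choice of formula matter?** With Bazett (exponent 1/2, baseline corrected QT 410 ms) the hidden rises for +5, +10 and +15 bpm are 15.5, 30.4 and 44.9 ms, about one and a half times the Fridericia values. This is a reason to fix the formula in advance.

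**Step 5: the visible threshold.** Raw QT of 500 ms corresponds to QTcF 500 / (60/50)^(1/3) = 471 ms at 50 bpm and 500 / (60/80)^(1/3) = 550 ms at 80 bpm. In the other direction, QTcF of 500 ms at 80 bpm is raw QT of 454 ms, which a raw limit of 500 ms does not flag.

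**The case against.** The strongest reply is that little depends on this table. The documents report no heart-rate effect of the drug at 12 h, so every millisecond figure above rests on an assumed shift. The safety analysis is descriptive, with six active participants per dose, one post-dose ECG and no tests. If the SD of QT change were 15 to 20 ms (also an assumption), a comparison of 6 active with 8 placebo participants would have a 95% half-width of 2.179 × SD × √(1/6 + 1/8), or about 18 to 24 ms. That is about as large as the distortion at +10 bpm. Heart rate is tabulated from the same ECGs, vital-sign heart rate is summarised at several times, the ECG data are listed by participant, and the investigator reviews each tracing. The protocol promises no QTc, so the SAP does not contradict it. SAP section 3 also allows further analyses if the study report identifies them.

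Much of this stands as a limit on weight. The size is conditional, the illustration takes Fridericia as the true relation, and no firm QT conclusion could come from this sample either way. It does not remove the problem. The distortion is a bias rather than noise, and it can be removed from data already collected. Where the analysis consists of reading means and individual values, those values should be interpretable. A reader who sees a rate shift in Table 6.1 still cannot correct QT per participant from the planned tables. QTc computed later from the listings would be an unplanned analysis, and unless the formula is fixed before lock it would be chosen with the data in view.

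**Conclusion.** The concern holds. For repolarisation the plan relies on uncorrected QT alone, and neither document contains a QTc variable or formula, although ECG change and PCSA are primary endpoints. Under the assumed baseline and shifts of -10 to +15 bpm, the spurious raw QT change runs from about +23 to -27 ms, and a true QTcF rise of about 10 to 29 ms could go unseen at +5 to +15 bpm. If the drug does not change heart rate, this bias in the comparison with placebo is zero; the documents do not settle which case applies.

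The effect is confined to the QT part of the ECG endpoint. The heart-rate, PR and QRS summaries stand, as does individual ECG review, and no sample size or error rate changes. The sponsor should make the change, but the endpoint as a whole does not fail without it.

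**What to change.** Before database lock:

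1. In SAP section 12.6, name one correction formula, for example Fridericia, QTcF = QT / (60/HR)^(1/3), and derive QTc from the QT and heart rate of the same recording.
2. Add a QTc table beside Table 6.4 with value, absolute and relative change from baseline, and PCSA. Keep the raw QT table.
3. In SAP section 19, pre-specify QTc PCSA criteria, including one based on change from baseline, in line with the other ECG parameters. The thresholds are the sponsor's to set, since protocol section 10.1.4 describes PCSA criteria as "defined by the Sponsor for clinical laboratory tests, vital signs, and ECG parameters".
4. Reconcile those criteria with the item "Potentially clinically significant ECG abnormalities" in the protocol's stopping rules, so that the two documents use the term consistently.

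The cost is one derived variable, one table and a short addition to section 19. No new data are required, because QT and heart rate are already collected on the same ECG.

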### 12.7 Clinical safety laboratory assessment

The Hematology and Chemistry parameters are collected at Screening and Visit 3.

They are:

#### Hematology:

- Erythrocytes
- Hemoglobin
- Hematocrit
- Leukocytes
- Monocytes
- Neutrophils
- $\ \ Eosinophils$
- Basophils
- LymphocytesPlatelets

### Chemistry:

- Creatinine Clearance
- Potassium
- Chloride
- Sodium
- Calcium
- Alanine Aminotransferase
- Aspartate Aminotransferase
- Amylase
- Glucose (at Screening and Visit 3)

They will be presented like Vital Signs, but with one table for Hematology, one for Chemistry.

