## **Description of Sites/Facilities Enrolling Participants**

Three investigational sites will participate.

Participants will be recruited via investigator's patient register or via advertising.

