## 11.2 Appendix 2: Clinical safety laboratory tests

The tests detailed in Table 1 will be performed by local laboratories

Additionally, if laboratory results not specifically required by the study protocol are used to make either a study intervention decision or response evaluation, the results must be entered into the eCRF.

Protocol-specific requirements for inclusion or exclusion of participants are detailed in Section 5 of the protocol.

Additional tests may be performed at any time during the study as determined necessary by the investigator or required by local regulations.

The investigator (or medically qualified designee) must document their review of each laboratory safety report (e.g., hematology, chemistry, pregnancy).

Table 1 - Protocol-required laboratory assessments

Laboratory assessments	Parameters
Serology	• HIV
	• HbsAg
	
 
Hepatitis C Ab
 

Hematology	• Red blood cell (RBC) count
	
 
Hemoglobin
 

• Hematocrit

• Platelet count

• White blood cell (WBC) count with differential: neutrophils, lymphocytes, monocytes, eosinophils and basophils

Clinical chemistry

- Creatinine (including glomerular filtration rate calculation);
- Serum electrolytes: potassium, chloride, sodium, calcium;
- Liver function tests: aspartate aminotransferase (AST), alanine aminotransferase (ALT);
- Amylasemia
- Glycemia

Urinalysis Pregnancy test

• β-human chorionic gonadotropin (HCG) for women of childbearing potential (only at screening for WOCBP)

Other test

• Rapid Antigen test for SARS-CoV-2 (if required by standard practice of site)

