### 9.4 Derived and Computed Variables

For any variable, the baseline value is defined as the last observation before IMP injection.

The time will be split into 3 periods (epochs):

- before treatment (screening)
- during treatment (from IMP injection to 7 days after IMP injection date)

after treatment

The following PK parameters will be calculated from measured plasma concentrations for each participant:

- Maximum observed concentration (Cmax)
- Time of maximum observed concentration (Tmax)
- Area under the curve (AUC0-t)
- Terminal Half-life (T1/2)

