#### **Table TTT. Weight over Time**

#### 12.5 Vital Signs

The vital signs are systolic blood pressure, diastolic blood pressure and heart rate. They are measured as follows:

Visit	Timepoint
Screening	-
Visit 2	Pre-Dose
	1h Post-Dose
	2h Post-Dose
	4h Post-Dose
	8h Post-Dose
	12h Post-Dose
	24h Post-Dose
Visit 3	_

The following will be presented for each vital sign:

- value (mean, SD, etc.)
- absolute change from baseline (mean, SD, etc.)
- PCSA (frequencies and percentages)

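### AST, ALT and amylase come from local laboratories at three sites but are averaged without ULN scaling, so if the laboratories' limits differ, dose-group means can reflect site mix

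*SAP*

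**What the plan says.** - **Where the tests are run.** Protocol 11.2: "The tests detailed in Table 1 will be performed by local laboratories". That table includes AST, ALT and amylasemia. The synopsis states: "Three investigational sites will participate".
- **What is reported.** SAP 12.7, on chemistry: "They will be presented like Vital Signs, but with one table for Hematology, one for Chemistry". The SAP 12.5 layout summarises each value by mean and SD and then gives "absolute change from baseline (mean, SD, etc". The hematology template in SAP 12.7 is headed in measurement units. SAP 12.6 adds a relative change for ECG only.
- **Which endpoint this serves.** Protocol 3.2.1 makes the laboratory parameters, ALT, AST and amylasemia among them, a primary endpoint, assessed "from D-7 to D8: Mean changes number of PCSA, Percentage of participants with PCSA".
- **When.** SAP 12.7: "The Hematology and Chemistry parameters are collected at Screening and Visit 3". Under SAP 9.4, "the baseline value is defined as the last observation before IMP injection". There is therefore one scheduled baseline and one scheduled post-dose value.
- **Thresholds.** For these enzymes all are ULN multiples. Entry requires AST and ALT below 1.5 ULN and amylase below 1 ULN (Protocol 5.1, I14 and I15). The amylase DLT is 3 ULN or more (Protocol 4.6.1). The PCSA limits are above 3 ULN for AST or ALT and 1.5 ULN or more for amylase (SAP 19).
- **Site control.** Protocol 6.3 and SAP 5.2 describe a list built on dose escalation and sentinel participants, used in order of randomization. Neither mentions stratification by site, and the SAP plans no by-site summary.

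**The concern.** Two laboratories with different upper limits for an enzyme may be reporting on different scales. The plan allows for this wherever a cut-off matters, by using ULN multiples. The means and mean changes are the exception: they average the reported units over whichever laboratories handled the samples.

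Each dose level has six active participants, cohorts fill one after another, and nothing stated keeps the site mix equal between doses. No tests are planned, so readers will judge any dose pattern by eye across the columns of Table 7.2. That table gives them no means of separating dose from laboratory. What is at stake is how a descriptive part of a primary endpoint is read. No decision rule is involved.

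**Working it through.** **Inputs from the documents.** Four cohorts of 6 active and 2 placebo: 4 x (6 + 2) = 32, which reproduces the planned total. That gives 24 active, 6 per dose, and 8 pooled placebo. Three sites, local laboratories.

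**Inputs assumed.** The documents give no ULNs or assays. I take one laboratory per site, ULNs of 60, 100 and 120 U/L, and the same true change d (in ULN multiples) for every participant.

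**Formula.** Mean raw change = sum over sites of (n_site x d x ULN_site) / 6. On the ULN scale the mean change is d for every site mix.

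**Results.**

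| True rise d | Mix 4:1:1 | Mix 2:2:2 | Mix 1:1:4 | xULN scale |
|---|---|---|---|---|
| 0.5 xULN | (120 + 50 + 60)/6 = 38.3 U/L | (60 + 100 + 120)/6 = 46.7 U/L | (30 + 50 + 240)/6 = 53.3 U/L | 0.50 |
| 0.1 xULN | (24 + 10 + 12)/6 = 7.7 U/L | (12 + 20 + 24)/6 = 9.3 U/L | (6 + 10 + 48)/6 = 10.7 U/L | 0.10 |
| 0 | 0 | 0 | 0 | 0 |

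The gap between the opposite mixes is 15 U/L at d = 0.5 and 3 U/L at d = 0.1. The ratio is 320/230 = 1.39 in both cases.

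**Range over the assumed ULN spread.** Take ULNs of 100/sqrt(r), 100 and 100 x sqrt(r), where r is the highest-to-lowest ratio. The apparent ratio of the 1:1:4 dose to the 4:1:1 dose, when the true ratio is 1, is:

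| r | 1 | 1.2 | 1.5 | 2 | 3 |
|---|---|---|---|---|---|
| Apparent ratio | 1.00 | 1.10 | 1.22 | 1.40 | 1.69 |

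**Ordering.** With assumed ULNs of 80, 100 and 120:
- A dose with +0.20 xULN and mix 1:1:4 shows 0.20 x (80 + 100 + 480)/6 = 22.0.
- A dose with +0.22 xULN and mix 4:1:1 shows 0.22 x (320 + 100 + 120)/6 = 19.8.

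The larger true change appears smaller.

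**Mean values.** These need no drug effect to be exposed. With the same three ULNs and everyone at 0.5 xULN, the mean runs from 0.5 x 90 = 45 (mix 4:1:1) to 0.5 x 110 = 55 (mix 1:1:4).

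**No drug effect.** If one laboratory analyses both of a participant's samples, a constant offset cancels in the change, and a scale factor multiplies zero. The expected mean change is 0 for every mix. It moves only if baseline and Visit 3 come from different laboratories. For example, an assumed 10-unit offset in 3 of 6 baselines shifts the mean change by 3 x 10/6 = 5 units. Protocol 8 lets qualifying routine results obtained before consent serve for screening, so this is possible. It is not the expected course, because Protocol 8.5.1 takes the safety bloods at the screening visit.

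**The case against.** The strongest reply is that the premise is not documented. No ULN, assay or between-site difference is given. One laboratory per site is inferred from the local testing and the number of sites. Protocol 8.1.4 refers to a laboratory manual that may set common methods. If the scales agree, the effect is nil. This stands, and the point is conditional for that reason.

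A reader might infer that the mean change does depend on site mix, or that site mix could produce a dose trend by itself. The documents do not support either. Change is within participant, so with one laboratory at both visits a scale difference only stretches or shrinks a real change. A misleading trend would need a real effect, differing scales and unequal site mixes together. Nor do the documents show that the pooled placebo group has a different mix: placebo is drawn two per cohort from the same four cohorts.

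The size is also open to challenge. A rise of 0.5 xULN is large for the only scheduled post-dose sample. D8 ± 2 days is 5 to 9 days after injection on D1. At the roughly 13-hour subcutaneous half-life in Protocol 2.1, that is 120/13 to 216/13, or about 9 to 17 half-lives. This too stands, which is why the 0.1 xULN case is shown beside it.

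Finally, the quantities with a decision role (entry, DLT, PCSA) are already ULN-scaled, individual chemistry data are listed, no tests are run, and absolute-unit summaries match Protocol 10.1.4. All correct. This limits the harm to the reading of descriptive means and argues for adding rows instead of replacing any. It does not show that the raw-unit means can be compared between doses.

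**Conclusion.** The point holds in conditional form. The plan pools AST, ALT and amylase from local laboratories at three sites into dose-level means and absolute changes, and it states neither normalisation nor site stratification. If the reference limits differ, the mean values, and the size and ordering of any real mean change, can depend on site mix. For the opposite mixes 4:1:1 and 1:1:4, the apparent ratio between two equally affected doses runs from 1.00 (identical limits) to 1.69 (threefold spread). In U/L, under assumed limits of 60, 100 and 120, the gap is 15 U/L for a rise of 0.5 xULN and 3 U/L for a rise of 0.1 xULN.

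These figures rest on assumed ULNs, assumed site mixes, and an effect proportional to the local ULN. PCSA counts and the amylase DLT are unaffected. This is a cheap improvement to a descriptive summary; no analysis is invalidated.

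**What to change.** In SAP 12.7, Table 7.2, add rows for AST, ALT and amylase giving the value and the change from baseline as multiples of the ULN of the laboratory that analysed each sample. Keep the raw-unit rows. Show the local ULN beside each result in Listing 16.2.15.

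Table 7.2.1 needs no change: it is a PCSA-only table, and its limits for these enzymes are already ULN multiples.

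The cost is a few extra table rows and one derived variable. The local ULNs are already needed for the entry criteria, the PCSA flags and the amylase DLT, so no new data are collected and no sample-size figure changes.
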